5.7.3.2. Vital Signs and Physical Examination Findings

Continuous vital sign parameters including temperature, respiratory rate, weight, pulse, blood pressure (systolic and diastolic), and Body Mass Index (BMI) will be summarized at each assessment time point. Body Mass Index will be calculated as weight (kg)/(height (m))², at each time point that body weight is measured. The height measurement collected at screening will be used in the calculation. Change from baseline will be summarized through Week 28 and from Week 28 through Week 60 for the main study, and from Week 52 through Week 112 for participants in the LTE period. Descriptive statistics (mean, standard deviation, median, minimum and maximum) will be presented.

Incidence of treatment-emergent clinically important abnormal vital signs during intervention, as defined in [Table 3](#), will be summarized for participants who had a baseline assessment and at least 1 postbaseline assessment for that vital sign. A listing of participants with treatment-emergent clinically important abnormality in vital signs will be presented.

Table 3: Clinically Important Abnormal Limits for Vital Signs

Vital Sign	Criteria
Pulse	>115 bpm and with >30 bpm increase from baseline
	<50 bpm and with >20 bpm decrease from baseline
Systolic blood pressure	>150 mm Hg and with >40 mm Hg increase from baseline
	<90 mm Hg and with >30 mm Hg decrease from baseline
Diastolic blood pressure	>95 mm Hg and with >30 mm Hg increase from baseline
	<50 mm Hg and with >20 mm Hg decrease from baseline
Interarm blood pressure	interarm blood pressure absolute difference ≥ 15 mmHg in systolic blood pressure at 3 consecutive visits
Temperature	>38.4°C and with $\geq 1^{\circ}\text{C}$ increase from baseline
Weight	increase 10% from baseline
	decrease 10% from baseline
Respiratory rate	>20 breaths per minute

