3. OBJECTIVE AND ENDPOINTS

Objectives	Endpoints
Primary	
To evaluate the efficacy of guselkumab compared to placebo, in combination with a 26-week glucocorticoid (GC) taper regimen, in adult participants with new-onset or relapsing giant cell arteritis (GCA).	The proportion of participants achieving GC-free remission at Week 28
Secondary	
To evaluate the efficacy of guselkumab compared to placebo, in combination with a 26-week GC taper regimen, in adult participants with new-onset or relapsing GCA as measured by alternative definitions of GC free remission, GC-sparing effects, and prevention of disease flares.	
The proportion of participants achieving GC-free remission from Week 28 by visit through Week 52
 
The proportion of participants achieving GC-free remission and normalization of erythrocyte sedimentation rate (ESR) at Week 28 and by visit through Week 52
 
The proportion of participants achieving GC-free remission and normalization of C-reactive protein (CRP) at Week 28 and by visit through Week 52
 
The proportion of participants achieving GC-free remission and normalization of both ESR and CRP at Week 28 and by visit through Week 52
 
The cumulative GC dose through week 28 and through Week 52
 
The time to first GCA disease flare or discontinuation of study intervention due to AE of worsening of GCA through Week 28 and through Week 52
 
The number of GCA disease flares or discontinuation of study intervention due to AE of worsening of GCA through Week 28 and through Week 52

To evaluate the safety of guselkumab, in combination with a 26-week GC taper	Number/proportion of participants with treatment-emergent adverse events (TEAEs) through Week 60

Objectives	Endpoints
regimen, in adult participants with new-onset or relapsing GCA.	
Number/proportion of participants with TEAEs by system organ class with a frequency threshold of 5% or more through Week 60
 
Number/proportion of participants with treatment-emergent serious adverse events (SAEs) through Week 60
 
Number/proportion of participants with clinically significant abnormalities in vital signs, laboratory safety tests through Week 60

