8.1.1. GCA Disease Signs and Symptoms

Efficacy of guselkumab in GCA will be assessed from the presence of GCA activity including investigator assessment of signs and symptoms of GCA.

Evaluation of clinical signs and symptoms by the dedicated Clinical Assessor at every study visit according to the SoA will include the following ([Hellmich 2020](#)).

Key symptoms

- Persistent localized headache, often in the temporal area, consistent with GCA
- Constitutional symptoms (eg, fatigue/malaise) could be considered features of a flare only if they occur in combination with elevated ESR and/or CRP.
- Jaw and/or tongue claudication
- Acute visual symptoms such as amaurosis fugax, acute visual loss, diplopia

- Symptoms of PMR such as recent discreet proximal musculoskeletal symptoms including aching and stiffness about the upper arms, posterior neck, pelvic girdle, and/or lumbar region often associated with morning stiffness, gelling, and/or functional limitations
- Limb claudication, myocardial and cerebrovascular symptoms

Key signs on clinical examination

- Tenderness and / or thickening of the superficial temporal arteries with or without reduced pulsation
- Scalp tenderness
- Bruits (particularly in the axilla)
- Reduced pulses/blood pressure of the upper limbs
- Pathological findings during ophthalmologic examination including anterior ischemic optic neuropathy, oculomotor cranial nerve palsy/palsies, central retinal artery occlusion, branch retinal artery occlusion and/or choroidal ischemia.

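### Two of the seven vital-sign criteria in SAP Table 3 (interarm systolic difference and respiratory rate) have no baseline condition, so an unchanged entry value can be reported as treatment-emergent

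*SAP*

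**What the plan says.** Protocol section 3 lists as a secondary safety endpoint: "Number/proportion of participants with clinically significant abnormalities in vital signs, laboratory safety tests through Week 60". SAP section 5.7.3.2 turns the vital-sign part of this into a summary of treatment-emergent abnormalities, worded as "Incidence of treatment-emergent clinically important abnormal vital signs during intervention", and refers to Table 3 for their definition.

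Most rows of Table 3 depend on baseline. The first pulse row, for example, reads ">115 bpm and with >30 bpm increase from baseline". Two rows do not:

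- Interarm pressure: "interarm blood pressure absolute difference ≥ 15 mmHg in systolic blood pressure at 3 consecutive visits".
- Respiratory rate: ">20 breaths per minute".

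The only other use of baseline is in the denominator: the incidence "will be summarized for participants who had a baseline assessment and at least 1 postbaseline assessment for that vital sign". That asks for a baseline reading to exist. It does not ask for the reading to be within the limit.

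**The concern.** Calling a finding treatment-emergent tells the reader that it was absent, or milder, before dosing. For these two rows the criterion cannot establish that. A participant whose arms already differ by 25 mmHg at Week 0, and still differ by 25 mmHg at Weeks 4, 8 and 12, meets the interarm criterion with no change at all. So does a participant who breathes at 22 per minute at entry and throughout.

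The interarm row deserves more attention in this disease. Protocol section 8.1.1 names among the key signs of GCA "Reduced pulses/blood pressure of the upper limbs", and inclusion criterion 4 now accepts imaging evidence that is not confined to the cranial arteries. The row that bears most directly on new large-vessel change is therefore one that, as written, cannot separate new findings from old ones.

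**Working it through.** The plan states no figure for this point, so there is nothing to reproduce. The check has four steps.

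**1. Table 3, row by row.**

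| Vital sign | Limit | Change from baseline |
|---|---|---|
| Pulse | yes | yes |
| Systolic pressure | yes | yes |
| Diastolic pressure | yes | yes |
| Temperature | yes | yes |
| Weight | no | yes |
| Interarm systolic difference | yes | **no** |
| Respiratory rate | yes | **no** |

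Two of seven have no baseline term.

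**2. Search for a rule elsewhere that supplies it.**

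- SAP 5.7.2 defines treatment-emergent by timing, and for adverse events only.
- SAP 5.8.2.1 applies the term to a measurement (antibodies) and requires change: negative before dosing and positive after, or a two-fold rise in titer. An unchanged titer counts as negative. The two Table 3 rows depart from that logic.
- SAP 5.7.3.1 and 5.7.3.3 plan shift tables from baseline for laboratory grades and for the C-SSRS. None is planned for vital signs, and the interarm difference is not among the continuous parameters named in 5.7.3.2.
- The SAP does not say whether pre-dose visits can count toward the three. If screening and Week 0 both counted, a single post-dose reading at Week 4 would complete the run.

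**3. Weight of one participant.** Planned arms are 34 and 17 (SAP section 3).

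- Guselkumab: 1/34 = 2.9 percentage points.
- Placebo: 1/17 = 5.9 percentage points.

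**4. How surely an unchanged difference is flagged (illustration on assumed inputs).** Assume a constant true difference μ and independent normal visit-to-visit noise with SD σ. A visit is over the limit if |μ + noise| ≥ 15. Take 14 post-baseline visits (Weeks 4 to 52 and Week 60) and flag any three in a row. Results are from 200,000 simulated participants; neither μ nor σ comes from the documents.

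| μ (mmHg) | σ (mmHg) | Flagged as written | Flagged if baseline must also be <15 |
|---|---|---|---|
| 20 | 3 | 1.000 | 0.048 |
| 20 | 5 | 0.996 | 0.158 |
| 20 | 8 | 0.965 | 0.257 |
| 25 | 3 | 1.000 | 0.000 |
| 25 | 5 | 1.000 | 0.023 |
| 25 | 8 | 0.999 | 0.105 |
| 0 | 3 to 8 | at most 0.003 | at most 0.002 |

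Hand check for μ = 20, σ = 5: P(baseline < 15) = Φ((15 − 20)/5) = Φ(−1) = 0.159, and 0.996 × 0.159 = 0.158, as in the table. The three-visit rule screens out noise well when there is no true difference, but it does almost nothing to screen out a difference that was there at entry.

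**The case against.** The best reply is that Table 3 supplies only the limits, and that the sentence introducing it separately requires the abnormality to be treatment-emergent. Asking for a baseline reading of the same vital sign would then serve to judge emergence. A programmer could reasonably work that way. But the sentence points to Table 3 for the definition, and five of the seven vital signs there carry their own baseline term, which suggests that the table is meant to settle the matter. Two programmers could produce two different tables, and the literal one is wrong for the label.

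It is also fair to say that the consequence is small. The summary is descriptive, with no test or decision attached. Flagged participants are listed individually, so in a trial of about 51 each case can be looked up. Protocol section 9.4.5 asks only for the percentage beyond clinically important limits, so absolute limits do fit the protocol; the mismatch is with the label that the SAP adds. New vascular disease is also looked for by the clinical assessor and by change in the PET score. All of this stands, and it limits the weight of the point.

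Three stronger readings are tempting, and the documents do not support them:

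- A reader might infer that a fixed interarm difference is common in this population, so that many participants would be miscounted. Protocol 8.1.1 lists the sign without saying how frequent or how permanent it is. Inclusion criterion 3 still requires at least one Domain I point, the non-cranial imaging route came in only with Amendment 5, and exclusion criteria 1, 3 and 4 may remove some participants with arterial disease.
- A reader might infer a bias against guselkumab. The rule is the same in both arms and randomization balances carriers in expectation; what remains is chance imbalance, with only 17 planned on placebo.
- A reader might extend the arterial example to respiratory rate. It does not apply there; the parallel case is simply a rate already above 20 at entry.

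**Conclusion.** The point holds as a defect in a stated rule. For interarm systolic difference and respiratory rate, an unchanged entry value in either arm meets the SAP criterion and would be reported as treatment-emergent. Each such participant contributes 2.9 points (guselkumab) or 5.9 points (placebo) to the incidence for that row, assuming the planned 34 and 17. The total effect cannot be sized, because the documents give no prevalence of either finding at entry. On the assumed differences of 20 to 25 mmHg and noise SD of 3 to 8 mmHg, a carrier is flagged with probability about 0.97 to 1.00. The effect is confined to a descriptive secondary safety summary; the primary and other efficacy analyses are unaffected. It is worth correcting because the label is wrong for those cases and the data to correct it are already collected.

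**What to change.** In SAP Table 3:

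- **Interarm difference:** absolute systolic difference of 15 mmHg or more at three consecutive post-baseline visits, and below 15 mmHg at baseline.
- **Respiratory rate:** above 20 per minute post-baseline, and not above 20 per minute at baseline.
- State that screening and Week 0 do not count toward the three visits.
- Show participants already over either limit at baseline in a separate row, by arm.

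Baseline is defined in SAP 5.1, and Protocol 8.2.2 has blood pressure taken in both arms for the first measurement at each visit, so the cost is table wording and programming. There are two downsides. Reported incidence may fall slightly, and worsening of a difference already present at entry will be seen only in the separate row. A single noisy baseline reading will also let some unchanged participants through: 0.05 to 0.26 of those with a true 20 mmHg difference in the illustration above, against 0.97 to 1.00 as the rule stands.

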5.7.3.3. Columbia-Suicide Severity Rating Scale

The C-SSRS will be used as a screening tool to prospectively evaluate suicidal ideation and behavior among study participants. The C-SSRS measures 5 possible levels of suicidal ideation and 4 possible suicidal behaviors, as well as non-suicidal self-injurious behavior. The assessment is a fully-structured, participant self-report C-SSRS questionnaire, including standardized questions, follow-up prompts, error handling routines, and scoring conventions. Two versions of the C-SSRS will be used in this study, the *Lifetime* version and the *Since Last Contact* version. The *Lifetime* version will be conducted during the screening visit and the *Since Last Contact* version will be conducted at all other visits.

At the screening visit, the C-SSRS should be completed as the first assessment after signing informed consent and before any other tests, procedures, or other consultations. For subsequent visits, the C-SSRS should be completed after all PROs and before any other tests, procedures, or other consultations. Participants will be interviewed by the investigator or trained study site personnel in a private, quiet place.

The following are C-SSRS categories and have binary responses (yes/no). A “yes” response to any C-SSRS category will be assigned a score as below:

Suicidal Ideation (1-5)

1 = Wish to be Dead

2 = Non-specific Active Suicidal Thoughts

3 = Active Suicidal Ideation with Any Methods (Not Plan) without Intent to Act

4 = Active Suicidal Ideation with Some Intent to Act, without Specific Plan

5 = Active Suicidal Ideation with Specific Plan and Intent

Suicidal Behavior (6-10)

6 = Preparatory Acts or Behavior

7 = Aborted Attempt

8 = Interrupted Attempt

9 = Actual Attempt (non-fatal)

10 = Completed Suicide

If no events qualify for a score of 1 to 10, a score of 0 will be assigned (0=“Negative result [no suicidal ideation or behavior]”). Higher scores indicate greater severity.

The summary for suicidal ideation and behavior will be based on the safety analysis set. Suicidal ideation and behavior will be summarized based on the most severe/maximum post baseline C-SSRS outcome or AE of suicidal ideation, suicidal behavior excluding completed suicide, or completed suicide through Week 28 or through Week 60 for the main study, and from Week 52 through Week 112 for participants in the LTE period. The baseline is defined as the most severe/maximum C-SSRS score at either screening or Week 0.

The maximum score assigned for each participant will also be summarized into one of three broad categories: No suicidal ideation or behavior, suicidal ideation, suicidal behavior. A shift table for change in C-SSRS categories of no suicidal ideation or behavior, suicidal ideation, and suicidal behavior from baseline through Week 28 and through 60 for the main study, and from Week 52

through Week 112 for participants in the LTE period will be presented, where the baseline category is based on C-SSRS score and the post baseline is based on C-SSRS or AE data.

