8.2.6. Columbia-Suicide Severity Rating Scale

No signal of suicidal ideation and behavior has been observed in the clinical trials of guselkumab to date. However, in light of reports concerning suicidal ideation and behavior in patients with plaque PsO treated with an IL-17R antagonist (brodalumab), the C-SSRS will be used as a screening tool to prospectively evaluate suicidal ideation and behavior among study participants (Rodriguez 2019).

The C-SSRS measures 5 possible levels of suicidal ideation and 4 possible suicidal behaviors, as well as non-suicidal self-injurious behavior. The C-SSRS is an investigator-administered questionnaire (Mundt 2013; Posner 2011). Two versions of the C-SSRS will be used in this study, the *Lifetime* version and the *Since Last Contact* version. The *Lifetime* version will be conducted during the screening visit and the *Since Last Contact* version will be conducted at all other visits.

The investigator or trained study-site personnel will interview the participant and complete the C-SSRS. The C-SSRS will be provided in the local languages in accordance with local guidelines.

At the screening visit, the C-SSRS should be completed as the first assessment after signing informed consent and before any other tests, procedures, or other consultations. For subsequent visits, the C-SSRS should be completed after all PROs and before any other tests, procedures, or other consultations. Participants will be interviewed by the investigator or trained study site personnel in a private, quiet place.

At the conclusion of each assessment, the trained personnel administering the C-SSRS will determine the level of suicidal ideation or behavior, if any. They will then determine the next course of action if any level of suicidal ideation or behavior is reported. The participant should not be released from the site until the C-SSRS has been reviewed by the investigator and the participant's risk has been assessed and follow-up determined, as appropriate.

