At screening (within the last 6 months) and Week 0, participants with a C-SSRS rating of Ideation level 4 or 5 (ie, Suicidal Ideation with Intention to Act, Suicidal Ideation with Specific Plan and Intent), or suicidal behavior (actual suicide attempt, interrupted suicide attempt, aborted suicide attempt, or preparatory behaviors for making a suicide attempt), must be determined to not be at risk by the investigator based on an evaluation by a mental health professional (eg, psychiatrist, psychologist, or appropriately trained social worker or nurse) in order to be randomized.

Participants with C-SSRS ratings of Ideation level 1-3 (ie, Wish to be Dead, Non-Specific Active Suicidal Thoughts, Active Suicidal Ideation with Any Methods (Not Plan) without Intent to Act) or non-suicidal self-injurious behavior must be determined not to be at risk by the investigator in order to be randomized in the study. Any questions regarding eligibility of such participants should be discussed with the medical monitor or designee.

For each C-SSRS assessment after Week 0, the following actions should be taken, if applicable:

- No suicidal ideation or behaviors (including self-injurious behavior without suicidal intent): No further action is needed
- Suicidal ideation levels 1-3 or non-suicidal self-injurious behavior: Participant risk is assessed by the investigator
- Suicidal ideation levels 4 or 5 or any suicidal behavior: Participant risk assessed and referral to a mental health professional.

Interruption or the discontinuation of study treatment should be considered for any participant who reports suicidal Ideation level 4 (some intent to act, no plan), Ideation level 5 (specific plan and intent), or any suicidal behavior (actual suicide attempts, interrupted attempts, aborted attempts, or preparatory actions) on a postbaseline (after Week 0) C-SSRS assessment and who is deemed to be at risk by the investigator based upon evaluation by a mental health professional. If a participant can be adequately treated with psychotherapy and/or pharmacotherapy then the participant, at the discretion of the investigator, may be continued with treatment if agreed to by

the medical monitor or designee. Discussion of such participants with the medical monitor or designee is required (see Section 7.1). The final decision on suitability for continuing in the study will be made by the investigator.

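### The C-SSRS shift table sets a baseline that includes lifetime history against on-study time only, so an on-study event no worse in category than that history does not show as worsening

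*SAP*

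**What the plan says.** SAP 5.7.3.3 and protocol 8.2.6 agree on the instrument. The Lifetime "version will be conducted during the screening visit", and the Since Last Contact version is used at all other visits, Week 0 included.

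The SAP then fixes the reference point: "The baseline is defined as the most severe/maximum C-SSRS score at either screening or Week 0". It attaches no recall period to the screening score.

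Scores run from 0 to 10: 0 is a negative result, 1 to 5 are ideation and 6 to 10 are behavior. The SAP plans "A shift table for change in C-SSRS categories of no suicidal ideation or behavior, suicidal ideation, and suicidal behavior from baseline through Week 28", and also through Week 60 and, for LTE participants, from Week 52 through Week 112. It adds that "the baseline category is based on C-SSRS score and the post baseline is based on C-SSRS or AE data".

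For eligibility the protocol looks at a shorter period. Section 8.2.6 introduces its rule on the more severe ratings with "At screening (within the last 6 months) and Week 0", and exclusion criterion 17 uses the same 6-month window.

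**The concern.** A shift table is read as change from the pre-treatment state, which requires the two sides to cover comparable periods. Here they do not. Participants are at least 50 years old (inclusion criterion 2), so the Lifetime version looks back over at least 50 years, while the post-baseline side covers at most 60 weeks of the main study.

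Remote history does not keep a person out of the trial. Exclusion 17 concerns the last 6 months and also requires that the investigator confirm risk after an evaluation by a mental health professional. People with an old episode can therefore be randomized, and that episode then sets their baseline row.

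At stake is the reading of the only planned C-SSRS table that conditions on baseline. On-treatment ideation in someone with an old episode of ideation would read as stable. An old episode that simply does not recur would read as improvement, in either arm. The protocol uses the C-SSRS to look prospectively for suicidality, and this table would serve that purpose poorly for anyone with history.

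**Working it through.** The SAP gives no figure to reproduce here. The check is an enumeration under its own scoring.

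**Inputs**
- Categories (SAP 5.7.3.3): none = 0, ideation = 1 to 5, behavior = 6 to 10.
- Baseline: maximum of the screening (Lifetime) score and the Week 0 (Since Last Contact) score.
- Post-baseline: worst on-study outcome from the C-SSRS or adverse event data.

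**Step 1. Category level.** Take a participant whose baseline is set by lifetime history.

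| Lifetime category | On-study category | Shift shown |
|---|---|---|
| Ideation | Ideation | No change |
| Ideation | Behavior | Worsening |
| Behavior | Ideation | Improvement |
| Behavior | Behavior | No change |
| Ideation or behavior | None | Improvement |

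Of the four rows with an on-study event, three show no worsening. A participant with lifetime behavior is already in the worst category and can never show worsening.

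**Step 2. Score level.** Let the lifetime score run over 1 to 9 (10 is a completed suicide) and the on-study score over 1 to 10. That gives 9 × 10 = 90 pairs.
- Ideation to ideation: 5 × 5 = 25, no change.
- Ideation to behavior: 5 × 5 = 25, worsening.
- Behavior to ideation: 4 × 5 = 20, improvement.
- Behavior to behavior: 4 × 5 = 20, no change.

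Totals: 45 no change, 20 improvement and 25 worsening. These are unweighted counts of pairs, not probabilities. In 20 of the 45 no-change pairs (10 within ideation, 10 within behavior) the on-study score is higher than the lifetime score. The three-category grouping contributes to hiding those pairs, so they cannot be put down to the Lifetime baseline alone.

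**Step 3. A recent baseline.** If only recent history counted, a participant with remote history alone would have baseline 0. All 10 possible on-study scores would then move to a worse category, and the absence of an event would read as no change.

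**Step 4. Weight of one participant.** With the planned 34 guselkumab and 17 placebo participants (SAP section 3), one misplaced person is 1/34 = 2.9% of one arm or 1/17 = 5.9% of the other. A chance difference of one or two people with old history between arms would be visible in the table for reasons unrelated to treatment.

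**Step 5. Extension.** The LTE shift table is in the same paragraph and no separate C-SSRS baseline is given for it, so the same comparison appears to carry over to Weeks 52 to 112.

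**The case against.** The strongest reply is that no event is lost. Post-baseline visits use Since Last Contact, so a positive post-baseline rating is an on-study event by construction. It counts in the post-baseline column of the shift table whatever the baseline row. It also appears in the maximum post-baseline summary, which does not depend on baseline, and in the SAP 5.7.2 listing of participants with suicidal ideation or behavior. Protocol 8.2.6 sends new or worsened findings that the investigator judges clinically significant to the adverse event form, and so into the treatment-emergent tables. The results are descriptive, and no test or stopping rule uses the shift. The protocol also reports no suicidality signal in guselkumab trials to date. All of this stands and limits the point to how one table is classified.

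A second reply is that the protocol's 6-month wording might show that the screening rating meant is the 6-month one. That wording governs who may be randomized. The SAP's baseline sentence does not carry the limit over, and its own text puts the Lifetime version at screening. Read as written, lifetime history enters the baseline.

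A reader might go further and infer that any new event in anyone with remote history is masked, or that the shift table is the only output separating new from old suicidality, so that on-treatment onset is hidden. The documents do not support either inference. Lifetime ideation followed by on-study behavior, the gravest of these shifts, still shows as worsening, and the outputs listed above report the events.

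**Conclusion.** The point holds within narrow bounds. As written, the shift table compares lifetime history with on-study time. It shows an on-study event as no change or improvement whenever that event is no worse in category than the history, and it shows improvement for remote history without recurrence. This follows from a stated rule, not from a missing detail. It affects one descriptive safety table in the main study and, since no other baseline is defined, apparently in the LTE. Efficacy, sample size and participant management are untouched.

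The number affected cannot be computed. The documents give no prevalence of lifetime ideation or behavior, so any headcount would rest on an assumed rate. A masked event also needs both a history and an on-study event of equal or lower category, and that joint count may be zero. The conclusion rests on reading the SAP's baseline sentence literally. It does not depend on any prevalence, because one affected participant is enough to be misplaced.

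**What to change.** For the shift table only, define the baseline category as the worst of two ratings: the 6 months before screening, which is the window already used in exclusion 17 and protocol 8.2.6, and Week 0. Report lifetime history as a separate baseline row. Leave the maximum post-baseline summary as it is. State the baseline for the LTE shift table explicitly.

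The documents show that a 6-month judgment is needed for eligibility, but not that it is held as its own field. If it is not, use the Week 0 Since Last Contact score alone. That matches the SAP's general rule in section 5.1, which takes the closest measurement at or before first dose. Its limit is that it covers only the interval since screening, up to 6 weeks, so ideation present shortly before screening would not count at baseline.

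The cost is a sentence or two in the SAP and minor programming. The preferred version depends on whether the 6-month rating was captured, and the fallback does not.
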